2. SUMMARY OF KEY PROTOCOL INFORMATION

2.1. Changes to the Protocol Defined Statistical Analysis Plan

There is one change to the originally planned statistical analysis specified in the protocol (Dated: 15-Sep-2016). For the secondary endpoint of the number of instructions (0, 1 or 2 times) from the HCP which are needed to demonstrate correct inhaler use, tracked changes were not copied through to the final document. As such the analysis stated in the protocol (logistic regression) is not appropriate and instead the analysis will be performed using Wilcoxon signed rank test as this was the originally planned analysis.

2.2. Study Objective(s) and Endpoint(s)

Objectives	Endpoints
Primary Objectives	Primary Endpoints

 To compare the number of critical errors made by COPD patients, after a subject has read the respective patient information leaflet(s) (PIL), for each treatment option tested 	
 The percentage of subjects making at least one critical error after reading the PIL(s)
Secondary Objectives	Secondary Endpoints

 To compare the number of critical errors made by COPD patients after instruction from the Healthcare Professional (HCP) for each treatment option tested 	
 The percentage of subjects making at least one critical error after the: 
 first instruction from the HCP second instruction from the HCP

 To compare the number of overall (critical and non-critical) errors made by COPD patients, after a subject has read the PIL(S) or after Instruction from the HCP for each treatment option tested 	
 The percentage of subjects making at least one overall error after reading the PIL(s) The percentage of subjects making at least one overall error after the first instruction from the HCP The percentage of subjects making at least one overall error after the second instruction from the HCP

 To compare the number of instructions (maximum of 2) from a HCP which is needed to demonstrate correct inhaler use 	
 The number of instructions (0, 1 or 2 times) from the HCP which are needed to demonstrate correct inhaler use

 To compare the Training/Teaching Time required to demonstrate correct inhaler use 	
 The total amount of time taken to demonstrate correct inhaler use (T1+T2). The amount of time taken to read the patient information leaflet and demonstrate correct inhaler use (T1) The amount of time taken to be given instruction by the HCP (up to 2 times) on use of the inhaler and to demonstrate correct inhaler use (T2)

 Preference attributes for each treatment option tested 	
 Treatment preference, from questionnaire for: Number of steps required to take COPD medication Over all treatment preference

2.3. Study Design

Overview of Study Design and Key Features	

The flowchart illustrates the study design process. It starts with V0 (COPD patients screened for inclusion). A green arrow indicates that V0 and V1 can be completed on the same day. The process then moves to V1, where subjects receive their first treatment. This is followed by an assessment for inhaler errors (critical and overall) on Treatment 1, including reading the PIL(s) and receiving up to 2X instruction from the HCP. This is followed by the second treatment, another assessment for inhaler errors on Treatment 2, and a final V1 assessment where the subject completes a preference questionnaire. Below this, two sub-studies are detailed. Sub Study 1 compares ELLIPTA (Treatment option 1) to DISKUS + HandiHaler combination (Treatment option 2). Sub Study 2 compares ELLIPTA (Treatment option 1) to Turbuhaler + HandiHaler combination (Treatment option 3). Each sub-study involves a PIL, a stopwatch, and the respective inhaler combinations. Preference questionnaires (PREF 1, 2 for Sub Study 1; PREF 3, 4 for Sub Study 2) are completed after each treatment.
	

Design Features
	
The study will be conducted as a multi-centre, randomised, open-label, placebo-device, cross-over study, with a 2x2 complete block design.
 
It will comprise of two sub studies:
 
 • Sub-study 1 will compare ELLIPTA (Treatment option 1) to DISKUS + HandiHaler combination (Treatment option 2) • Sub-study 2 will compare ELLIPTA (Treatment option 1) to Turbuhaler + HandiHaler combination (Treatment option 3). 
The study has 2 visits (V0 and V1) and both can be completed on the same day. Each sub-study may run independently or in parallel of the other sub study. Each will start dependent on the availability of the placebo DPIs required for that sub-study. The data from the 2 sub studies may be reported independently and as each sub study completes and the data for that sub study have been cleaned. The database will be locked when all of the sub-studies have completed and all data are cleaned.

Dosing
	
 • Not applicable as this is a placebo study.

Overview of Study Design and Key Features				
Treatment Assignment	Sub-study 1 Treatment Sequences			
	Sequence	Period 1	Period 2	Preference Questionnaire
	A	ELLIPTA	DISKUS + HandiHaler	1
	B	DISKUS + HandiHaler	ELLIPTA	2
	C	ELLIPTA	DISKUS + HandiHaler	2
	D	DISKUS + HandiHaler	ELLIPTA	1
	Sub-study 2 Treatment Sequence			
	Sequence	Period 1	Period 2	Preference Questionnaire
	E	ELLIPTA	Turbuhaler + HandiHaler	3
	F	Turbuhaler + HandiHaler	ELLIPTA	4
	G	ELLIPTA	Turbuhaler + HandiHaler	4
	H	Turbuhaler + HandiHaler	ELLIPTA	3

2.4. Statistical Hypotheses

The primary purpose of this study is to assess the number of critical errors made by COPD patients, after a subject has read the patient information leaflet(s) (PIL) for each treatment option tested. This is a superiority study.

There are two sub-studies and these will be analysed separately. There is no overlap of subjects and so these are considered independent. Hence there will be no adjustment for multiplicity.

The primary endpoint is the percentage of subjects making at least one critical error after reading the PIL(s) on Treatment Option 1 compared with each of Treatment Option 2 (Sub-study 1) and Treatment Option 3 (Sub-study 2).

For each sub-study, the null hypotheses are no difference between treatment options:
 $H_0: p_1 = p_i; i=2, 3$

The alternative hypothesis is that there is a difference between treatment options.
 $H_A: p_1 \neq p_i; i=2,3$

Where treatment $p_1 = \text{ELLIPTA}$, $p_2 = \text{DISKUS + HandiHaler}$ and $p_3 = \text{Turbuhaler + HandiHaler}$

3. PLANNED ANALYSES

3.1. Final Analyses

No interim analysis is planned.

The final planned primary analyses will be performed after the completion of the following sequential steps:

1. All subjects have completed the study as defined in the protocol for both sub-study 1 and sub-study 2.
2. All required database cleaning activities have been completed and final database release and database freeze has been declared by Data Management.
3. All criteria for unblinding the randomisation codes have been met.
4. Randomisation code schedules for both sub-studies have been distributed according to RandAll NG procedures.

4. ANALYSIS POPULATIONS

Population	Definition / Criteria	Analyses Evaluated
All Subjects Enrolled (ASE)	
 • All participants who sign the ICF and for whom a record exists in the study database, including screen failures and any subject who was not screened but experienced an SAE between the date of informed consent and the planned date of the Screening visit. 	
 • Study population • Reason for withdrawal prior to randomisation
Randomised	
 • All participants who were randomised. 	
 • No formal analysis will be performed on this population
Intent-to-treat (ITT)	
 • All randomised subjects who made at least one critical error assessment from one treatment option device. A subject who is recorded as a screen or run-in failure and also randomised will be considered to be randomised in error provided they have not performed any error assessments. 	
 • Study population • Efficacy • Subject disposition • Safety • Inclusion, exclusion and randomisation criteria deviations
Safety	This population will be the same as the Intent-to-treat population.	

NOTES :

- Please refer to [Appendix 11](#): List of Data Displays which details the population to be used for each displays being generated.

4.1. Protocol Deviations

- Important protocol deviations (including deviations related to study inclusion/exclusion criteria, conduct of the trial, patient management or patient assessment) will be summarised and listed.
- Protocol deviations will be tracked by the study team throughout the conduct of the study in accordance with the Protocol Deviation Management Plan.
 - Data will be reviewed prior to unblinding and freezing the database to ensure all important deviations are captured and categorised on the protocol deviations dataset.
 - This dataset will be the basis for the summaries and listings of protocol deviations.
- A separate summary and listing of all inclusion/exclusion criteria deviations will also be provided. This summary will be based on data as recorded on the inclusion/exclusion page of the eCRF.

5. CONSIDERATIONS FOR DATA ANALYSES AND DATA HANDLING CONVENTIONS

Table 1 provides an overview of appendices within the RAP for outlining general considerations for data analyses and data handling conventions.

Table 1 Overview of Appendices

Section	Component
11.1	Appendix 1: Protocol Deviation Management
11.2	Appendix 2: Time & Events
11.3	Appendix 3: Treatment Phases
11.4	Appendix 4: Data Display Standards & Handling Conventions
11.5	Appendix 5: Derived and Transformed Data
11.6	Appendix 6: Premature Withdrawals & Handling of Missing Data
11.7	Appendix 7: Multicenter Studies
11.8	Appendix 8: Examination of Covariates, Subgroups & Other Strata
11.9	Appendix 9: Model Checking and Diagnostics for Statistical Analyses
11.10	Appendix 10: Abbreviations & Trade Marks
11.11	Appendix 11: List of Data Displays
11.12	Appendix 12: Example Mock Shells for Data Displays

6. STUDY POPULATION ANALYSES

The study population analyses will be based on the ITT population unless otherwise stated.

Table 2 provides an overview of the planned study population analyses, with full details of data displays being presented in Appendix 11: List of Data Displays.

Table 2 Overview of Planned Study Population Analyses

Display Type	Data Displays Generated		
	Table	Figure	Listing
Subject Disposition and Demography			
Study Populations (ASE)	Y		
Attendance at Each Clinic Visit	Y		
Screening Failures	Y		Y
Treatment Status and Reasons for Discontinuation of Study Treatment	Y		Y
End of Study Record by Treatment period	Y		
Subject Disposition at Each Treatment Period	Y		
Reasons for withdrawal	Y		Y(ASE)
Number of Subjects by Country and Centre	Y		
Summary of Age Ranges	Y (ASE)		
Demographic Characteristics	Y		Y
Demographic Characteristics by Country	Y		
Race and Racial Combinations	Y		
Race and Racial Combinations Details	Y		Y
Protocol Deviations			
Important deviations	Y		Y
Inclusion/Exclusion/Randomisation Criteria Deviations	Y		Y
Treatment Misallocations			Y
Medical Condition & Concomitant Medications			
Medical Conditions (Current/Past)	Y		Y
Family History of Cardiovascular Risk Factors	Y		Y
COPD History and COPD Exacerbation History (Only one listing required)	Y		Y
Smoking History and Status	Y		Y
COPD Medications	Y		Y
Non-COPD Medications	Y		Y
Relationship between ATC Level 1, ingredient and verbatim text non-COPD medications only			Y
Devices			
Naivety to Inhaler Devices	Y		Y

6.1. Disposition

The study population summary will show the number of subjects overall who were enrolled, the number of screen failures and the number with each reason for screen failure. It will also show the number of subjects in each sub-study and overall who were randomised and who were in the ITT population.

The reasons for withdrawal summary will show the number and percentage of subjects who completed the study, who withdrew prematurely from the study and who reported each primary and sub-reason for withdrawal. This will be presented for each sub-study and overall.

6.2. Medical Conditions

The number and percentage of subjects reporting each current medical condition will be presented by sub-study and overall. This table will include a category of ‘Cardiovascular Risk Factors’. All medical conditions must be summarised on this table regardless of frequency.

This will be repeated for past medical conditions.

6.3. Concomitant Medications

Non-COPD medications will be summarised by Anatomical-Therapeutic-Chemical (ATC) level 1 and ingredient. COPD medications will be summarised by Respiratory Medication Class (RMC) and ATC, and will be derived for each COPD concomitant medication. Multi-ingredient medications will be presented according to their combination ATC classification rather than the classifications of the ingredients. These tables will be presented by sub-study and overall.

COPD and non-COPD medications will be listed together.

A listing of the relationship between ATC Level 1, ingredient and verbatim text will be produced for non-COPD medications only.

7. PRIMARY STATISTICAL ANALYSES

7.1. Efficacy Analyses

7.1.1. Overview of Planned Efficacy Analyses

The primary efficacy analyses will be based on the ITT population, unless otherwise specified.

[Table 3](#) provides an overview of the planned efficacy analyses, with full details of data displays being presented in [Appendix 11: List of Data Displays](#).

Table 3 Overview of Planned Primary Efficacy Analyses

	Absolute			
	Stats Analysis		Summary	
	T	F	T	F
At least one critical error				
Percentage of subjects making at least one critical error after reading the PIL(s)	Y		Y	Y

NOTES :

- T = Table, F = Figure, Y = Yes display generated.
- Stats Analysis = Represents TF related to any formal statistical analyses (i.e. modelling) conducted.
- Summary = Represents TF related to any summaries (i.e. descriptive statistics) of the observed raw data.

7.1.2. Planned Efficacy Statistical Analyses

Primary Statistical Analyses
Endpoint(s)

 • Percentage of subjects making at least one critical error after reading the PIL(s)
Model Specification

 • The primary endpoint of the percentage of subjects making at least one critical error after reading the PIL(s) will be analysed using the Intent-to-treat population. • This endpoint will be analysed using conditional logistic regression with subject as fixed strata, and treatment option and period as fixed effects. • Country will be included in the model providing there are sufficient subjects distributed to enable the model to run. If the model will not run with country in the model then country will be removed from the model.
Model Checking & Diagnostics

 • Refer to Appendix 9: Model Checking and Diagnostics for Statistical Analyses.
Model Results Presentation

 • The odds ratio, 95% CI and p-value will be presented for the comparison between treatment options. It will be based on a two-sided hypothesis testing approach of superiority.
SAS Code

 • Logistic regression will be used to calculate the odds ratio with 95% CI and p-value. The following SAS code will be used: <pre> proc logistic data=errors; class device period country; strata subject; model error = country device period / expb; oddsratio device; run; </pre> 
error is derived as shown in Section 11.5.3

Sensitivity and Supportive Statistical Analyses

- A sensitivity analysis will be performed using the Cochran-Mantel-Haenszel (CMH) test. The CMH test serves as a stratified approximation to the Mainland-Gart test, a variation of a one-sample chi-square test that accounts for study inhaler sequence (period). A subject who had an error with both devices or who had no errors with both devices does not provide any information about the superiority of either device. Only those subjects who had error(s) in one device and had no error in the other device are counted for in the Mainland-Gart test.
- SAS code for the CMH test is provided below:

```
proc freq data=errors (where=(err_ord^=0));
    tables seq*err_ord/cmh;
run;
```

As with the main analysis, country will be included as a covariate if sufficient data is available as described above. err_ord is derived as shown in Section [11.5.3](#)

8. SECONDARY STATISTICAL ANALYSES**8.1. Efficacy Analyses****8.1.1. Overview of Planned Secondary Efficacy Analyses**

The secondary efficacy analyses will be based on the Intent-to-treat population, unless otherwise specified.

[Table 4](#) provides an overview of the planned secondary efficacy analyses, with further details of data displays being presented in [Appendix 11: List of Data Displays](#).

Table 4 Overview of Planned Secondary Efficacy Analyses

	Absolute			
	Stats Analysis	Summary		Individual
	T	T	F	L
Number of critical errors made after 1st Healthcare Professional (HCP) instructions				
The percentage of subjects making at least one critical error after the first instruction from the HCP	Y	Y	Y	
Number of overall errors made				
Percentage of subjects making at least one overall error after reading the PIL(s)	Y	Y	Y	
Percentage of subjects making at least one overall error after the first instruction from the HCP	Y	Y	Y	
Number of instructions (maximum of 2) from the HCP				
Number of instructions from the HCP	Y	Y	Y	Y
Total Training/Teaching time required				
Total time taken to demonstrate correct inhaler use (T1+T2)	Y	Y	Y	Y

	Absolute			
	Stats Analysis	Summary		Individual
	T	T	F	L
Preference attributes				
Treatment preference for number of steps required to take medication	Y	Y		Y
Treatment preference for taking COPD medication	Y	Y		Y

NOTES :

- T = Table, F = Figure, L = Listing, Y = Yes display generated.
- Stats Analysis = Represents TFL related to any formal statistical analyses (i.e. modelling) conducted.
- Summary = Represents TFL related to any summaries (i.e. descriptive statistics) of the observed raw data.
- Individual = Represents TFL related to any displays of individual subject observed raw data.

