10.2. Sample Size Determination

The sample size calculation for each sub-study is based on the primary endpoint, the percentage of subjects making at least one critical error in each device combination (Ellipta or DISKUS - HandiHaler or Turbuhaler - HandiHaler) after reading the patient information leaflet(s).

Based on the results from studies 201301 and 201330, a range of critical error rates (at least one critical error using each device after reading the patient information leaflet) for each of the treatment options (ELLIPTA, DISKUS - HandiHaler and Turbuhaler - HandiHaler) were explored.

Using 10000 simulations, a total of 72 subjects in each sub-study will provide at least 90% power to show a statistically significant difference between the critical error rate of each of the paired treatment options (Sub-study 1: Treatment option 1 vs. Treatment Option 2; Sub-study 2: Treatment option 1 vs. Treatment Option 3) assuming the following true critical error rates.

Treatment Option 1:	Treatment Option 2:	Treatment Option 3:
ELLIPTA Critical Error Rate	DISKUS - HandiHaler Critical Error rate	Turbuhaler - HandiHaler Critical Error rate
11%	>=37%	>=37%
10%	>=35%	>=35%
9%	>=34%	>=34%
8%	>=32%	>=32%
7%	>=31%	>=31%
6%	>=29%	>=29%

The error rates for the combined treatment options were based on the studies 201301 and 201330 and a conservative assumption that the critical error rate for the combined treatment was the same as the critical error rate for a single device i.e. subjects who made errors made them on both devices.

Conditional logistic regression and a two-sided 5% significance level were used as the analysis method in the simulations. No withdrawal is expected in this single visit study however up to 80 subjects may be randomised to each sub-study to ensure we have 72 evaluable subjects in each sub-study.

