Overview	Key Elements of the RAP																								
	
 • Subjects will be randomised 1:1:1:1 to each of the four treatment sequences in both sub study 1 and sub study 2. The randomisation schedules for each sub study will be created independently. 160 participants will be randomised (80 in each sub study), such that approximately 144 are evaluable (72 in each sub study). • The study has three treatment periods. The first two treatment periods are a 2x2 complete block design to test the ELLIPTA against DISKUS + HandiHaler or Turbuhaler + HandiHaler. The third treatment period contains a questionnaire to assess subject preference. • Using 10000 simulations, a total of 72 subjects in each sub-study will provide at least 90% power to show a statistically significant difference between the critical error rate of each of the paired treatment options (Sub-study 1: Treatment option 1 vs. Treatment Option 2; Sub-study 2: Treatment option 1 vs. Treatment Option 3) assuming the following true critical error rates. 
  
 Treatment Option 1:	Treatment Option 2:	Treatment Option 3:	
   
 ELLIPTA Critical Error Rate	DISKUS + HandiHaler Critical Error Rate	Turbuhaler + HandiHaler Critical Error Rate	
 
 11%	>=37%	>=37%	
 
 10%	>=35%	>=35%	
 
 9%	>=34%	>=34%	
 
 8%	>=32%	>=32%	
 
 7%	>=31%	>=31%	
 
 6%	>=29%	>=29%	
  
	Treatment Option 1:	Treatment Option 2:	Treatment Option 3:	ELLIPTA Critical Error Rate	DISKUS + HandiHaler Critical Error Rate	Turbuhaler + HandiHaler Critical Error Rate	11%	>=37%	>=37%	10%	>=35%	>=35%	9%	>=34%	>=34%	8%	>=32%	>=32%	7%	>=31%	>=31%	6%	>=29%	>=29%
Treatment Option 1:	Treatment Option 2:	Treatment Option 3:																							
ELLIPTA Critical Error Rate	DISKUS + HandiHaler Critical Error Rate	Turbuhaler + HandiHaler Critical Error Rate																							
11%	>=37%	>=37%																							
10%	>=35%	>=35%																							
9%	>=34%	>=34%																							
8%	>=32%	>=32%																							
7%	>=31%	>=31%																							
6%	>=29%	>=29%																							

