11.5.3. Critical and Overall Errors

Critical and Overall errors

An ordinal variable (error) will be derived to indicate where a participant had any error, or any critical error whilst demonstrating correct device use. If the subject has an overall/critical error the error=Y whilst if they did not have an overall/critical error then error=N. The variables errty/errtycd will be used to determine whether the variable error is referring to a critical or overall error.

An ordinal variable (err_ord) will be derived to indicate the responses of critical error based on comparing responses for the device sequences used. This variable will be used in the sensitivity analysis for critical error data.

If the sequence of inhaler use is ELLIPTA in the 1st period and DISKUS + HandiHaler or Turbuhaler + HandiHaler in the 2nd period, then for critical error in relation to sequence:
 
 err_ord = -1, if subject had critical error in the 1st period but NOT in the 2nd period err_ord = 1, if subject had critical error in the 2nd period but NOT in the 1st period err_ord = 0, if subject had critical errors in BOTH periods or had NO critical errors in BOTH periods

If the sequence of inhaler use is and DISKUS + HandiHaler or Turbuhaler + HandiHaler in the 1st period and ELLIPTA in the 2nd period, then for each preference question:
 
 err_ord = 1, if subject had critical error in the 1st period but NOT in the 2nd period err_ord = -1, if subject had critical error in the 2nd period but NOT in the 1st period err_ord = 0, if subject had critical errors in BOTH periods or had NO critical errors in BOTH periods

The above method also applies to overall errors.

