11.11.2. Efficacy Tables

Overall Summary of Errors					
No.	Population	IDSL / TST ID / Example Shell	Title	Programming Notes	Deliverable
2.01	ITT	EFF_T01	Summary of Errors on ELLIPTA	Page by sub-study	SAC
2.02	ITT	EFF_T01	Summary of Errors on ELLIPTA by Country	Page by sub-study and country	SAC
2.03	ITT	EFF_T01	Summary of Errors on DISKUS + HandiHaler	Page by DISKUS + HandiHaler Errors, DISKUS Errors and HandiHaler Errors	SAC
2.04	ITT	EFF_T01	Summary of Errors on DISKUS + HandiHaler by Country	Page by DISKUS + HandiHaler Errors, DISKUS Errors, HandiHaler Errors and Country	SAC
2.05	ITT	EFF_T01	Summary of Errors on Turbuhaler + HandiHaler	Page by Turbuhaler + HandiHaler Errors, Turbuhaler Errors and HandiHaler Errors	SAC
2.06	ITT	EFF_T01	Summary of Errors on Turbuhaler + HandiHaler by Country	Page by Turbuhaler + HandiHaler Errors, Turbuhaler Errors, HandiHaler Errors and country	SAC
2.07	ITT	EFF_T06	Summary of Critical Errors	Page by sub-study and assessment	SAC
2.08	ITT	EFF_T06	Summary of Critical Errors by Country.	Page by sub-study, assessment and country	SAC

Overall Summary of Errors					
No.	Population	IDSL / TST ID / Example Shell	Title	Programming Notes	Deliverable
Primary Analysis Tables					
2.09	ITT	EFF_T04	Analysis of Percentage of Subjects making at least one Critical Error	Include analysis only if sufficient data is available for models to run. Page by sub-study and assessment	SAC
2.10	ITT	EFF_T07	Sensitivity Analysis of Percentage of Subjects making at least one Error after Reading the PIL(s)	Page by sub-study	SAC
Secondary Analysis Tables					
Number of Overall Errors					
2.11	ITT	EFF_T04	Analysis of Percentage of Subjects making at least one Overall Error	Include analysis only if sufficient data is available for models to run. Page by sub-study and assessment.	SAC
Training/Teaching Time Required					
2.12	ITT	EFF_T02	Summary and Analysis of Time (Minutes) Taken to Demonstrate Correct Inhaler Use	Page by sub-study and assessment.	SAC
Preference Attributes					
2.13	ITT	EFF_T03	Summary of Treatment Preference	Page by sub-study.	SAC
2.14	ITT	EFF_T05	Summary and Analysis of Number of Instructions from the HCP	Only if sufficient data is available. Page by sub-study.	SAC

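### The primary conditional logistic model often has no finite odds ratio at the planning rates (about 14-37% of trials at n=72), and the SAP does not say what is then reported

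*SAP*

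**What the plan says.** SAP 7.1.2 sets the primary model: "This endpoint will be analysed using conditional logistic regression with subject as fixed strata, and treatment option and period as fixed effects". It adds that "The odds ratio, 95% CI and p-value will be presented for the comparison between treatment options". The printed code is PROC LOGISTIC with a STRATA statement for subject, and it has no exact or penalised option. The text does not say whether the p-value is Wald, score, likelihood-ratio or exact.

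Two provisions deal with a model that fails. SAP 7.1.2 says "If the model will not run with country in the model then country will be removed from the model". The programming note for Table 2.09 in SAP 11.11.2, the primary table, says "Include analysis only if sufficient data is available for models to run". The rule of falling back to summary statistics is written for the first- and second-instruction endpoints and for overall errors (SAP 8.1.2.1, 8.1.2.2 and 9.1.1.1), not for the primary endpoint.

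A CMH test is planned as a sensitivity analysis and described as an approximation to Mainland-Gart. It uses err_ord from SAP 11.5.3. For the ELLIPTA-first order that section has "err_ord = -1, if subject had critical error in the 1st period but NOT in the 2nd period"; for the other order the signs are reversed.

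Protocol 10.2 states that "a total of 72 subjects in each sub-study will provide at least 90% power to show a statistically significant difference" and that "Conditional logistic regression and a two-sided 5% significance level were used as the analysis method in the simulations". The SAP synopsis plans that "160 participants will be randomised (80 in each sub study), such that approximately 144 are evaluable (72 in each sub study").

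**The concern.** With subject as stratum, only subjects who erred on one treatment and not the other contribute. Device and period are then two parameters fitted to two proportions, one per order, so the model is saturated and a single empty discordant cell sends the device estimate to infinity. The scarce cell is ELLIPTA-only errors, so failure becomes likelier the better ELLIPTA performs.

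Neither failure rule helps. Country is constant within a subject and carries no information in a subject-stratified fit, so removing it cannot fill an empty cell. The Table 2.09 note only allows the analysis to be left out. It does not define a model that runs, and software can print estimates from a diverging fit. The primary odds ratio, interval and p-value would then be missing, meaningless, or picked once the data are known.

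**Working it through.** **Inputs.** Six planning rows, 11% v 37% down to 6% v 29% (Protocol 10.2). Equal allocation to four sequences (Protocol 7.2), hence 36 subjects per device order at n=72 and 40 at n=80. Two-sided 5% level. The documents give no within-subject correlation between ELLIPTA and the combination; independence is assumed first, then varied. No period effect is assumed.

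**The plan's own figure.** Simulated power at n=72 over the six rows:

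- likelihood-ratio test, device plus period: 96-97%
- exact conditional test: about 93-94%
- Wald, device only: 92-96%
- Wald, device plus period, separated fits counted as non-significant: about 58-82% (65-86% at n=80)

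The stated power of at least 90% is therefore reproduced by the first three. It is not reproduced by the last, which is the Wald result from the model as specified.

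**Chance of no finite odds ratio.** Let e and c be the ELLIPTA and combination error rates and m the number per order. Then pE = e(1-c) is the probability of an ELLIPTA-only error and pC = c(1-e) that of a combination-only error.

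P(no finite OR) = 1 - [1 - (1-pE)^m - (1-pC)^m + (1-pE-pC)^m]^2

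The terms in pC are negligible here (about 0.00001 or less). For 11% v 37%: pE = 0.11 x 0.63 = 0.0693; (1-0.0693)^36 = 0.0754; 1 - 0.9246^2 = 0.145.

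| Rates | pE | Expected ELLIPTA-only per 36 | P(none in one order) | No finite OR, n=72 | No finite OR, n=80 |
|---|---|---|---|---|---|
| 11 v 37% | 0.0693 | 2.49 | 0.075 | 14.5% | 11.0% |
| 10 v 35% | 0.0650 | 2.34 | 0.089 | 17.0% | 13.1% |
| 9 v 34% | 0.0594 | 2.14 | 0.110 | 20.8% | 16.5% |
| 8 v 32% | 0.0544 | 1.96 | 0.133 | 24.9% | 20.2% |
| 7 v 31% | 0.0483 | 1.74 | 0.168 | 30.8% | 25.7% |
| 6 v 29% | 0.0426 | 1.53 | 0.209 | 37.4% | 32.0% |

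Range over the unstated correlation at n=72 (first row to last row): phi = -0.1, 8-26%; phi = 0.1, 25-53%; phi = 0.2, 42-71%. At n=80, phi = 0.1 gives 20-47% and phi = 0.2 gives 37-67%.

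**What the open choice does.** Write the cells as ELLIPTA-only/combination-only in each order. The device log odds ratio is half the sum of the two log ratios.

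- *All cells filled, 2/12 and 3/12.* log OR = 0.5 x [ln(2/12) + ln(3/12)] = -1.589, so OR = 0.204. SE = 0.5 x sqrt(1/2 + 1/12 + 1/3 + 1/12) = 0.50. Wald p = 0.0015; exact p = 0.0007, 95% CI 0.059-0.61.
- *One cell empty, 0/12 and 3/12.* The fit does not converge: OR 0.004, SE 10, Wald p = 0.60 after 8 iterations; OR 0.0006, SE 77, p = 0.92 after 12. The likelihood-ratio statistic is 2 x {[3 ln(3/15) + 12 ln(12/15)] - [12 ln(12/27) + 15 ln(15/27)]} = 22.1, p = 0.000003. Exact p = 0.00004, median-unbiased OR 0.15, upper 97.5% limit 0.41 (one-sided 95% limit 0.36).

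Across simulated separated trials at n=72, the likelihood-ratio test rejects in essentially 100% and the exact test in 99.6-100%.

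**The CMH test as coded.** In SAP 11.5.3 a combination-only error gives err_ord = +1 in both orders: it is the period 2 error when ELLIPTA comes first and the period 1 error when the combination comes first. Crossing sequence with err_ord therefore asks whether the two orders differ, not whether the devices do. pref_ord in SAP 11.5.4 is coded by period, as Mainland-Gart and Prescott tests need. In simulation at n=72 the test as coded rejects in 3-4% of trials; with err_ord coded by period it rejects in 95-97%. For cells 2/12 and 3/12, Fisher's test gives p = 1.0 on the table as coded and p = 0.0007 on the table coded by period.

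**The case against.** The SAP fixes the model and prints the code, and its synopsis says decisions on the final analysis are made before database freeze, so an after-the-fact choice is not inevitable. Table 2.09 does contain a rule, and shell EFF_T06 would still show both error percentages and the discordant counts. The planning rows are rates at which power suffices, not forecasts. Eighty subjects are to be randomised and no withdrawals are expected, so 11-32% is the fairer range. Several tests meet the stated power. The err_ord fault is separate from the separation problem. Naming the likelihood-ratio test would be simpler and slightly more powerful than exact inference.

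Much of this is fair. The n=80 figures belong beside the n=72 ones, the correlation is unknown, no power error is shown, and the likelihood-ratio test is a legitimate choice of p-value. It does not close the gap. Whether the model runs is known only once the data are fitted, and the trial is open-label. Omitting the primary analysis is not a substitute for it, and the counts in EFF_T06 carry no p-value or interval. A likelihood-ratio p-value alone leaves the promised odds ratio and interval unresolved. The err_ord fault matters here because it removes the one other planned test that might have been relied on.

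**Conclusion.** The concern holds and should be fixed. Under independence and the protocol's planning rates, the specified primary model has no finite device odds ratio in 14.5-37.4% of trials at n=72 and 11.0-32.0% at n=80. Positive within-subject correlation raises these shares and mild negative correlation lowers them without removing the problem. In those trials the plan as written gives no usable primary odds ratio, interval or Wald p-value and names no replacement. The sensitivity test as coded does not test the device effect. The evidence for a device difference would remain strong under a likelihood-ratio or exact test, so this is a defect in what is pre-specified and not in the design or sample size.

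**What to change.** In SAP 7.1.2, keep device and period. State that the primary device p-value, odds ratio and 95% CI come from exact conditional inference (exact Mainland-Gart) in every case, not only when the model fails, so that no data-dependent switch arises. When a discordant cell is zero, report the median-unbiased odds ratio with a one-sided interval and write down its level; a 97.5% limit matches the two-sided 5% test. State that the odds ratio is for making a critical error, ELLIPTA versus the combination, as in shell EFF_T04.

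If the CMH test is kept, code err_ord in SAP 11.5.3 by the period of the error, as pref_ord is in 11.5.4. In Protocol 10.2 and the SAP synopsis, state which test and model terms the power figure refers to; for the exact test with period it is about 93-94% at the listed rates, n=72, under independence.

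The cost is SAP wording, a few code lines and one clarification in the protocol, which would need the usual amendment handling; no extra subjects. The exact test is slightly conservative (about 93-94% power against 96-97% for the likelihood-ratio test). The interval remains one-sided in the same 14-37% of trials (11-32% at n=80): the change supplies a valid p-value and one finite limit, not a two-sided interval.
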